## 16.4. Secondary end-points

### 16.4.1. Analyses

In addition to the qualitative evaluation of the performance of the AP device, the percentage of time spent in each zone, and the visual evaluation provided by CVGA plots, other quantitative measures will be reported, analyzed and interpreted. They are presented in [Table 16–3](#). Unless indicated otherwise, the calculations are performed using CGM values.

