**Table 16–3: Secondary end-points measures**

Measure	Description
Averages	
Mean glucose level during the 24-hour closed-loop	Computed from CGM and then YSI values
Mean-pre meal glucose value	Computed 0-60 minutes before unannounced evening and morning meal
Mean-post meal glucose value	Computed 0-5 hrs after the evening and morning meal
Mean exercise glucose value	Computed value during the 30 min of exercise
Mean-pre-exercise glucose value	Computed 0-60 minutes before exercise
Mean-post exercise glucose value	Computed 0-3 hrs after end of exercise
Extremes	
% of time of glucose > 400 mg/dL	Computed from CGM and YSI values: analysis during 24 hour closed-loop, during night (12:00 am to 7:00 am) and during exercise
% of time of glucose ≥ 300 mg/dL	Computed from CGM and YSI values if duration is more than 1 hour: analysis during 24 hour closed-loop, during night (12:00 am to 7:00 am) and during exercise
% of time of glucose < 60 mg/dL	Computed from CGM and YSI values: analysis during 24 hour closed-loop, during night (12:00 am to 7:00 am) and during exercise
% of time of glucose ≤ 70 mg/dL	Computed from CGM and YSI values if duration is more than 1 hour: analysis during 24 hour closed-loop, during night (12:00 am to 7:00 am) and during exercise
Area under the curve per gram CHO	Computed from the beginning of a meal and continued for 5

Measure	Description
	hours
Area under the curve during exercise	Computed during exercise and for 3 hours following exercise
Area between the curve and nearest zone limit when outside the range [80-140] mg/dL	This will measure how much deviation from the zone. The analysis may be performed for the 24-hour closed-loop, for the night (12:00 am to 7:00 am), and during/following exercise and meals.
Total amount of insulin delivered and standard deviation of delivery amounts during the 24-hour closed-loop	Correspondence of total insulin delivered to total daily insulin (TDI)
Variability and risk assessment (*)	
Interquartile range	It measures the spread around the center of the desired zone, i.e. 110 mg/dL
LBGI: Low blood glucose index	Measures the frequency and extend of low blood glucose readings using CGM data
HBGI: High blood glucose index	Measures the frequency and extend of high blood glucose readings using CGM data
Blood glucose index: LBGI+HBGI	Measure the overall variability and the associated risk with hypoglycemia and hyperglycemia.

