#### 16.4.2. Details for calculations

*Inter-quartile range (IQR)*: It is a measure of the glucose variability. It is more appropriate than the glucose standard deviation because the glucose distribution is highly asymmetric; the hypoglycemic range is numerically narrower than the hyperglycemic range, so the distribution of the glucose values of a subject is typically skewed. The standard deviation of glucose values would be predominantly influenced by hyperglycemic excursion and would not be sensitive to hypoglycemia. Therefore, the inter-quartile range will be calculated. It is also called the mid-spread or middle fifty. It is a statistical dispersion being equal to the difference between the third and first quartile. It is a robust statistic.

$$IQR = Q_3 - Q_1 \quad (1)$$

Where:  $Q_3$  is the 75th percentile and  $Q_1$  is the 25th percentile

*Risk index (LBGI and HBGI):* In order to capture the glucose variability and its associated risks for hypoglycemia and hyperglycemia, the low blood glucose index (LBGI) and high blood glucose index (HBGI) will be calculated as follows:

Compute (2):

$$f(BG) = 1.509 \times [(\ln(BG)) 1.084 - 5.381] \quad (2)$$

The BG risk function is  $r(BG)$  using equation (3):

$$r(BG) = 10 \times f(BG)^2 \quad (3)$$

The left and right branches are separated as described by (4) and (5):

$$rl(BG) = r(BG) \text{ if } f(BG) < 0 \text{ and } 0 \text{ otherwise} \quad (4)$$

$$rh(BG) = r(BG) \text{ if } f(BG) > 0 \text{ and } 0 \text{ otherwise} \quad (5)$$

Given a series of CGM readings  $BG_1, BG_2, \dots, BG_n$ , the Low and High BG indices (LBGI and HBGI) are computed as the average of  $rl(BG)$  and  $rh(BG)$  respectively.

$$LBGI = \frac{1}{n} \sum_{i=1}^n rl(BG_i) \quad (6)$$

$$HBGI = \frac{1}{n} \sum_{i=1}^n rh(BG_i) \quad (7)$$

The BG risk index is then defined as:

$$BGRI = LBGI + HBGI \quad (8)$$

In essence, the LBGI and the HBGI split the overall glucose variation into two independent sections related to excursions into hypo- and hyperglycemia, and at the same time equalize the amplitude of these excursions with respect to the risk they carry.

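### Table 16–3 lists the area outside [80-140] mg/dL without direction; as a single total it is dominated by highs and can fall while low area rises, so report the two sides separately

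*Combined protocol and SAP*

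**What the plan says.** Section 16.4.1, Table 16–3, has one row for the "Area between the curve and nearest zone limit when outside the range [80-140] mg/dL". Its description reads "This will measure how much deviation from the zone", followed by "The analysis may be performed for the 24-hour closed-loop, for the night (12:00 am to 7:00 am), and during/following exercise and meals". The breakdown is therefore by time window only, and it is optional. The data source is CGM by default: "Unless indicated otherwise, the calculations are performed using CGM values".

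The same table reports lows in other rows:

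- The percentage "of time of glucose < 60 mg/dL", from CGM and YSI, with no duration condition.
- The percentage "of time of glucose ≤ 70 mg/dL", from CGM and YSI, only if the duration is more than one hour.
- LBGI, described as "Measures the frequency and extend of low blood glucose readings using CGM data", with HBGI as its counterpart for highs.

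The two percent-time rows name the 24-hour closed loop, the night and exercise. The LBGI and HBGI rows and their formulas in section 16.4.2 name no window.

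Section 16.4.2 also explains why the interquartile range is preferred to the standard deviation: "the hypoglycemic range is numerically narrower than the hyperglycemic range", so a standard deviation in mg/dL would mainly reflect highs and respond poorly to lows.

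**The concern.** The study adds a fixed inhaled insulin dose before each meal. The hoped-for effect is less area above 140 mg/dL after meals, and the natural safety question is whether area below 80 mg/dL grows. An undirected area mixes the two on a raw mg/dL scale, where the low side has little room to contribute. Reported as a single figure, it could look better in sessions with more hypoglycaemia, and it would have the insensitivity to lows for which section 16.4.2 sets aside the standard deviation. What is at stake is the reading of a descriptive secondary measure, mainly in the post-meal windows. The primary end-points and the sample size are not affected.

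**Working it through.** The plan gives no value or threshold for this measure, so there is no stated figure to reproduce. The checks below use direct arithmetic.

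**1. Weight of one reading.** Deviation from the zone: d(g) = max(80 − g, 0) + max(g − 140, 0).

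- d(40) = 80 − 40 = 40 and d(180) = 180 − 140 = 40, so the two count equally.
- Under the plan's own risk function (section 16.4.2, equations 2 and 3, reading 1.084 as an exponent whose superscript was presumably lost in the text), r(40) = 36.4 and r(180) = 7.7. The ratio is about 4.7.

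**2. Share of lows implied by the predecessor study.** Table 3–1, entire closed loop, YSI: <70, 1%; <80, 5%; >140, 43%; >150, 36%; >180, 18%. Assume no reading below 40 mg/dL. Areas are time-averaged, in mg/dL.

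- Largest possible low area: (5% − 1%) × 10 + 1% × 40 = 0.4 + 0.4 = 0.8.
- Smallest possible high area: 18% × 40 + (36% − 18%) × 10 = 7.2 + 1.8 = 9.0.
- Lows as a share of the total: at most 0.8 / 9.8 = 8.2%.
- With a floor of 50 mg/dL: 0.4 + 1% × 30 = 0.7, and 0.7 / 9.7 = 7.2%.
- With the table's whole-percent rounding taken at its least favourable (<70, 1.5%; <80, 5.5%; >150, 35.5%; >180, 17.5%): low 0.4 + 0.6 = 1.0, high 7.0 + 1.8 = 8.8, share 1.0 / 9.8 = 10.2%.

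The same bound, with the 40 mg/dL floor, in the meal columns:

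- Breakfast (<70, 2%; <80, 7%; >150, 53%; >180, 35%): low 0.5 + 0.8 = 1.3; high 14.0 + 1.8 = 15.8; share at most 1.3 / 17.1 = 7.6%.
- Dinner (<70, 0%; <80, 4%; >150, 61%; >180, 28%): low 0.4; high 11.2 + 3.3 = 14.5; share at most 0.4 / 14.9 = 2.7%.

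**3. What this allows.** A 25% cut in the 24-hour high area of 9.0 removes 2.25. Low area could then rise from 0.8 to just under 0.8 + 2.25 = 3.05, or 3.8-fold, and the total would still fall.

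**4. When a trade lowers the total.** The profiles are illustrative: 110 mg/dL for the rest of 24 hours, areas in mg/dL × h.

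| Before | After | Total before | Total after |
|---|---|---|---|
| 4 h at 200 | 2 h at 200, 2 h at 50 | 4 × 60 = 240 | 120 + 60 = 180 (−25%) |
| 4 h at 180 | 2 h at 180, 2 h at 40 | 4 × 40 = 160 | 80 + 80 = 160 (no change) |
| 2 h at 160 | 2 h at 50 | 2 × 20 = 40 | 2 × 30 = 60 (worse) |

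The total falls only if the high area removed exceeds the low area added. In the first line it falls while LBGI rises from 0.01 to 1.89 and time below 60 mg/dL rises from 0 to 2/24 = 8.3%. Split by side, that line reads 240 to 120 above and 0 to 60 below, so the low excursion is visible.

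**5. What covers the post-meal windows.** The quantitative measures that Tables 16–2 and 16–3 name for the hours after a meal are percent time in [70-180], mean glucose, area under the curve per gram of carbohydrate, and this area. None separates lows from highs.

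**The case against.** The strongest reply has four parts.

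- **The text does not say that the two sides are added.** This stands. Nearest limit says only where each deviation is measured from. A single total is the natural reading of one undirected row, but it is an inference.
- **Lows are already reported.** This largely stands for the 24-hour period. Time below 60 mg/dL and LBGI would show many trades of highs for lows. Section 2.2 lists low CGM values and YSI values below 60 among the secondary endpoints, and the CVGA plots minimum and maximum on separate axes. But these are for 24 hours, the night or exercise, or they name no window. Section 2.2 also lists excursions outside the target ranges and their duration, which could cover the post-meal range, but without direction.
- **A lower total is not always misleading.** This stands. Take 5 h at 200 mg/dL (area 5 × 60 = 300) against 4 h at 185 plus 45 min at 55 (180 + 18.75 = 198.75). The plan's risk-weighted sum LBGI + HBGI also falls, from 2.43 to 2.01, although LBGI alone rises from 0.01 to 0.56.
- **Nothing is decided on this row.** This stands. The study is single-arm with one fixed inhaled dose, and no threshold or test is attached to the area. The comparison with IDE G110093 names 1- and 2-hour glucose, the 6-hour area under the curve, and glucose profiles.

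A reader might infer something stronger: that the combined area falls whether highs shrink or lows grow, and so rewards over-delivery of insulin. The documents do not support that. Added low area always raises the total, and an equal trade leaves it unchanged. Nothing in the plan scores a dose by this measure.

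**Conclusion.** The point holds as a gap in a descriptive secondary measure. Table 16–3 gives an area without direction. If it is reported as one total, lows would be at most about 8% of it over 24 hours on the predecessor study's figures (about 10% allowing for rounding), and the total can fall while low area rises. Other rows would expose many such trades over 24 hours, but none is specified for the post-meal windows, and the ≤70 mg/dL row is further limited to durations above one hour.

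The 8% rests on a 40 mg/dL floor, on YSI rather than CGM values, and on a study without inhaled insulin and with a different breakfast size. It shows how such a total behaves and does not predict this study's results. The size is that of a free improvement; no conclusion the plan sets out to draw depends on it.

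**What to change.** In Table 16–3, replace the row by two: area above 140 mg/dL and area below 80 mg/dL. Report each for the 24-hour closed loop, the night, each post-meal window and the exercise/post-exercise window, and state that they are read beside LBGI and HBGI. The total may still be shown, but not alone. The windows are already contemplated in the row as optional, so the change is to make them definite and to split by side. It costs one line of text and a small change to the calculation on CGM data already collected. No new data are needed.

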#### 16.4.2. Details for calculations

*Inter-quartile range (IQR)*: It is a measure of the glucose variability. It is more appropriate than the glucose standard deviation because the glucose distribution is highly asymmetric; the hypoglycemic range is numerically narrower than the hyperglycemic range, so the distribution of the glucose values of a subject is typically skewed. The standard deviation of glucose values would be predominantly influenced by hyperglycemic excursion and would not be sensitive to hypoglycemia. Therefore, the inter-quartile range will be calculated. It is also called the mid-spread or middle fifty. It is a statistical dispersion being equal to the difference between the third and first quartile. It is a robust statistic.

$$IQR = Q_3 - Q_1 \quad (1)$$

Where:  $Q_3$  is the 75th percentile and  $Q_1$  is the 25th percentile

*Risk index (LBGI and HBGI):* In order to capture the glucose variability and its associated risks for hypoglycemia and hyperglycemia, the low blood glucose index (LBGI) and high blood glucose index (HBGI) will be calculated as follows:

Compute (2):

$$f(BG) = 1.509 \times [(\ln(BG)) 1.084 - 5.381] \quad (2)$$

The BG risk function is  $r(BG)$  using equation (3):

$$r(BG) = 10 \times f(BG)^2 \quad (3)$$

The left and right branches are separated as described by (4) and (5):

$$rl(BG) = r(BG) \text{ if } f(BG) < 0 \text{ and } 0 \text{ otherwise} \quad (4)$$

$$rh(BG) = r(BG) \text{ if } f(BG) > 0 \text{ and } 0 \text{ otherwise} \quad (5)$$

Given a series of CGM readings  $BG_1, BG_2, \dots, BG_n$ , the Low and High BG indices (LBGI and HBGI) are computed as the average of  $rl(BG)$  and  $rh(BG)$  respectively.

$$LBGI = \frac{1}{n} \sum_{i=1}^n rl(BG_i) \quad (6)$$

$$HBGI = \frac{1}{n} \sum_{i=1}^n rh(BG_i) \quad (7)$$

The BG risk index is then defined as:

$$BGRI = LBGI + HBGI \quad (8)$$

In essence, the LBGI and the HBGI split the overall glucose variation into two independent sections related to excursions into hypo- and hyperglycemia, and at the same time equalize the amplitude of these excursions with respect to the risk they carry.

## 17.ACCESS TO SOURCE DATA / DOCUMENT

### 17.1. Electronic data

After the insertion of the 2 CGMs, the subject will be an outpatient for 2 to 3 days before the CRC closed-loop trial. Data from the CGM and insulin data during those few days will be collected for information purpose only.

There are two types of data collected from the in-patient phase of the study:

- Manually entered data in APS© MATLAB® file:
  - Time stamps meal, exercise, other events
  - YSI values transferred from paper print out
- Automatically generated:
  - APS© generated MATLAB® file with continuous glucose CGM and insulin data.

The MATLAB® file generated during the closed-loop, including the time stamped events can be converted into Excel for analysis once the trial has been completed. Patients are identified by numbers, and only the study coordinator is able to correlate the electronic file with the name of the patient. Data analysis is blind to the patient's name. There will be a Master Patient Log.

At the end of each trial with each subject, the electronic file is copied onto a Sansum computer which is backed up daily to an outside location. The Sansum computer is password protected and all the data are saved to a dedicated folder. Data are saved with an appropriate filename. Access to the data is controlled via password. Only restricted personnel has access to the data and there is an audit trail associated with all data entry, data changes and manipulations. Raw data are protected and cannot be altered. Hard copy print-out of the data are also generated as a back up at the time of completion of the trial (prior to conversion of the file into Excel).

### **17.2. Hard copy records**

All forms for the screening visit, the monitoring form, the clinical research forms (CRFs) and the informed consent are completed using a hard copy document. The record is the original hard copy document. All records are kept at Sansum in the study file. The records are kept indefinitely.

## **18.RECORD KEEPING**

All clinical hard copy forms and records are maintained by Sansum Diabetes Research Institute. They are locked and kept indefinitely.

All electronic records will be stored both on the study computer and will be transferred to a Sansum computer that is connected to a backup server at the end of each closed-loop session.

## **20.FINANCIAL DISCLOSURE**

This clinical trial is partly funded by the JDRF grant #17-2010-765. It is also actively supported by the Chemical Engineering department of the University of California, Santa Barbara, and Sansum Diabetes Research Institute.

Subjects will be paid \$400 to participate in this study; and there will be no cost to the subjects to participate in this study.

Study supplies are provided at no cost by Dexcom® Corporation for CGMs (Dexcom® G4® System) and Animas Corporation for insulin delivery pumps (OneTouch® Ping®) and finger stick glucose meter (OneTouch® Ultra®).

Financial disclosure of the Principle Investigator will be kept in the study file.

## **21.INVESTIGATOR’S BROCHURE**

The AP device User Manual to be used by the investigator can be found in Appendix 1 of the IDE application.

